Quasi-Desensitization Placebo Therapy (QDT). This form of placebo therapy has been commonly used in prior studies investigating behavioral interventions for insomnia^{9,13,51,52}. The therapist presents the QDT as a means to eliminate "conditioned arousal," occurring after nocturnal arousal using 8 sessions on a weekly basis. The therapist initially helps the subject to develop a chronological 12-item hierarchy of commonly practiced activities on awakening at night, like opening eyes and clock watching. As a next step, the subject develops 6 imaginal scenes of himself/herself engaged in neutral activities like reading a newspaper. The therapist then helps the subject pair the neutral scenes with the items from the 12-item hierarchy, which is then practiced by the subject ≥ 2 hours before bedtime.

- 2.2. Describe how randomization or other treatment assignment will be made. **Subjects will be block randomized using a computer generated randomizing sequence.** Participants are randomly assigned to the CBT-I group, or the QDT group. The study biostatistician will create randomization sequences by family history of alcoholism (separate sequences) using a pseudo-random number generator with block sizes of 4. Two boxes of sequentially numbered, sealed, opaque envelopes will be prepared using the randomization sequences and labeled "Family History" and "No Family History". At the time of randomization, the first envelope, in sequential order, is pulled from the appropriate box and opened to reveal the group assignment. All the staff conducting assessments will be blinded to the allocation of treatment arm with the exception of Dr.

[name], the BSM treatment provider, [name] the person overseeing treatment allocation, and [name], the monitor for BSM treatment for the study.

- 2.3. For retrospective research studies, provide the "look-back" period. (e.g., December 1, 1999 through December 31, 2008.) **N/A.**

3. **Study Duration**

- 3.1. Provide the estimated length of time to enroll all subjects and complete the study. **Five years.**
- 3.2. Explain the expected duration of subject participation including any follow-up. **Eight months.**
- 3.3. Specify the projected date of completion of the proposed study. **Dec. 2018.**

4. **Drug Information.** Not Applicable.

5. **Investigational Device.** Not Applicable.

M. **Does this project involve international research?** YES NO

N. **Study Procedure.** Please see Table 1 for all the study-related procedures.

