
early phases of the study, using laboratory data, inclusion and exclusion criteria, and other person-specific information). Personnel involved will include the following: Principal investigator, study coordinator, behavioral sleep medicine practitioners associated with this study.

- 9.5.6. Include the breakdown of each individual's responsibilities:
 - 9.5.6.1. **Principal Investigator.** He may fulfill any of the roles required for the study, including, answering questions for prospective participants, informed consent procedure for participation for assessment for study entry, baseline assessments, assessments as part of the study visits, conducting the cognitive behavioral therapy sessions, scheduling the participant sessions, post-study assessments, conducting the urine drug screens, drawing blood and preparing the blood sample for storage in the freezer, coordinating clinical care with other providers.
 - 9.5.6.2. **Co-Principal Investigator, N/A**
 - 9.5.6.3. **Research Coordinator.** S/he will be involved in answering questions for prospective participants, informed consent procedure for participation for assessment for study entry, baseline assessments, assessments as part of the study visits including the urine drug screen test at baseline, drawing blood samples (after completion of the requisite training), scheduling the participant sessions, post-study assessments.
 - 9.5.6.4. **Additional research staff by title.** a. Phlebotomy – either [name] or a designated staff certified and IRB-approved to draw blood will conduct the blood draws and prepare the samples for the storage in the designated R & D freezer space; b. Certified Behavioral Sleep Medicine Provider: s/he will conduct the CBT-I and the QDT sessions for the participants; the Principal Investigator, [name] will conduct CBT-I or QDT as a backup provider.
- 9.6. Will informed consent be obtained from potential subjects prior to determining eligibility?
 YES NO N/A
 - 9.6.1. If no, provide justification and a HIPAA Waiver of Individual Authorization for Disclosure of Protected Health Information.
- 9.7. **Define when a subject is enrolled into the study, e.g. after the subject signs the informed consent or after randomized to treatment.** After he is randomized into a treatment arm.
- 9.8. Describe:

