4.1. **Include statistical power calculations and the assumptions made in making these calculations.** The following power calculations for Aims 1-3 assume the availability of 86 subjects who are eligible for randomization into one of two groups (n=43 per group). We assume a range of intra-class correlation of 0.1-0.5 and up to 10 follow-up measures per participant. The sample size is inflated to accommodate a 30% missing or dropout rate by 6 months based on rates over a similar period of time in previous studies⁵⁵. We consider a conservative adjustment in the two-sided level of significance, 0.025, to account for two hypothesis tests per Aim (3-month and 6-month outcome). Table 4 presents the detectable effect size based on the above assumptions for 90% and 80% power. The study will have 80% power to detect a moderate effect size of 0.50 standard deviations of a continuous outcome measure at 6 months assuming an intra-class correlation of 0.3. Table 5 presents the detectable effect in units applicable to each outcome based on the observed standard deviation from studies in the literature.

Power	Intra-class Correlation	Detectable effect size	
		3 months	6 months
80%	0.1	0.35	0.40
	0.3	0.48	0.50
	0.5	0.58	0.61
90%	0.1	0.40	0.41
	0.3	0.55	0.57
	0.5	0.66	0.70

(Assumptions: power=80%; n=30 per group after 30% attrition; 2-sided=0.05)

- Standard Deviation
- Insomnia Se
- Quality of Life
- Pooled within group standard deviation
- Pooled within group standard deviation (estimated from presented data)
- Pooled within group standard deviation for general health

Outcome	Pre-Post S.D. ^a	Detectable Difference
ISI ^b	3.809 ^d	1.90 points
Abstinent Days	15.96 ^e	7.98 %
Health Related QOL ^c	9.15 ^f	4.58 points

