- 4.2. **Define plans for data and statistical analysis, including key elements of the statistical plan, stopping rules and endpoints.** *Overview:* Our study proposes a longitudinal repeated-measures parallel-group design. This powerful design, with a baseline measurement and up to ten follow-up measures per participant over 6 months, allows for comparisons within each participant over time as well as across participants (treatment groups). The main analysis will look at differences between intervention groups in the changes in outcomes over time (i.e. insomnia severity, alcoholism-related outcomes and daily functioning). *Randomization:* Patients will be recruited and randomized as individuals. Allocation will be uniform across the two groups after suitable blocking and stratification on family history of alcoholism to ensure optimal balance of participant characteristics and to observe relationships between groups with and without a family history of alcoholism in the Exploratory Aim. Participants are randomly assigned to the CBT-I group, or the QDT group. The study biostatistician will create randomization sequences by family history of alcoholism (separate sequences) using a pseudo-random number generator with block sizes of 4. Two boxes of sequentially numbered, sealed, opaque envelopes will be prepared using the randomization sequences and labeled "Family History" and "No Family History". At the time of randomization, the first envelope, in sequential order, is pulled from the appropriate box and opened to reveal the group assignment. All the staff conducting assessments will be blinded to the allocation of treatment arm with the exception of [name], the BSM treatment provider, [name] the person overseeing treatment allocation, and [name], the monitor for BSM treatment for the study. *Preliminary Analyses:* All data, regardless of the format, will first be assessed by [name] and his mentors for missing data, distributions of all observed measures, and out-of-range values by means of conventional descriptive tables. SAS v9.3 will be our primary tool for these analyses as the software is both mature and well-documented⁵⁶. Next, we will employ raw and smoothed plots to visualize the individual and average trajectories of all repeated measures over time according to assigned treatment and by participant characteristics. All questions of data quality and integrity will be investigated before any statistical modeling, since complete and accurate data are essential for unbiased estimates and confidence intervals. We will compare all baseline variables across groups to check the adequacy of randomization. The baseline comparisons will be based on: 1) t-test or Wilcoxon rank sum tests for continuous variables depending on the symmetry of the distributions; 2) on logistic regression for binary or ordinal variables; and 3) on Poisson log-linear regression for count data. If imbalances are found at baseline, then the relevant variables will be treated as confounders in the analysis.

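### A fixed, published block size of 4 lets anyone who knows the earlier assignments in a stratum deduce about a third of allocations, and the listed staff roles make that knowledge plausible among those who control entry

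*Combined protocol and SAP*

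**What the plan says.** Section L.2.2, repeated in V.4.2, has the study biostatistician prepare a separate sequence for each family-history stratum "using a pseudo-random number generator with block sizes of 4". No other size is given. Neither section says that the size varies or is withheld from site staff. V.4.2 describes the ratio as equal: "Allocation will be uniform across the two groups after suitable blocking and stratification on family history of alcoholism". The assignments go into sequentially numbered, sealed, opaque envelopes, kept in two boxes labelled by stratum. Section V.4.1 plans 86 randomized, 43 per arm.

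On who knows the assignments, V.4.2 says: "All the staff conducting assessments will be blinded to the allocation of treatment arm with the exception of [name], the BSM treatment provider". The person overseeing allocation and the treatment monitor are also excepted. Section Q.9.5.6.4 says of the behavioral sleep medicine provider that "s/he will conduct the CBT-I and the QDT sessions for the participants", and that the principal investigator "will conduct CBT-I or QDT as a backup provider".

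On who controls entry, the list for the final eligibility determination (Q.9.5.5) reads: "Personnel involved will include the following: Principal investigator, study coordinator, behavioral sleep medicine practitioners associated with this study". The same titles appear for consent (Q.9.5.1), pre-screening (Q.9.5.2) and recruitment (Q.9.5.3). Section Q.9.5.6.1 lets the principal investigator take on any study role and names consent, baseline assessment, therapy sessions and scheduling among them. Under Q.9.7 a participant counts as enrolled only once randomized.

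**The concern.** A sealed opaque envelope conceals the next card only if that card cannot be worked out from the cards already opened. With a known block of 4 at 1:1, the fourth assignment in a block always follows from the first three, and the third follows whenever the first two match. Two strata do not prevent this, because family history is a study assessment and the boxes carry the stratum label.

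The weakness matters most when one person both sees past assignments and influences who enters and when. The role lists allow that overlap. Recruitment, consent and eligibility decisions all come before the envelope is opened. The interval before consent depends partly on staff availability (Q.9.8.2), and some eligibility items call for judgement, such as whether a medical condition is unstable (Q.2.1.2). At stake is the comparability of the arms at entry in a single-centre trial.

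**Working it through.** The plan states no predictability figure, so there is none to reproduce.

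**Inputs.** Block size 4 and two separate strata (L.2.2, V.4.2); equal allocation (V.4.2); 86 randomized (V.4.1). The observer is assumed to know every earlier assignment in the stratum, in order.

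**Certain allocations in a complete block.** Two A and two B can be ordered in 6 equally likely ways.

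| Position in block | Probability that the assignment is already certain | Probability that the best guess is right |
|---|---|---|
| 1 | 0 | 1/2 |
| 2 | 0 | 2/3 |
| 3 | 1/3 (first two match) | 1/3 × 1 + 2/3 × 1/2 = 2/3 |
| 4 | 1 | 1 |

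- Certain: (0 + 0 + 1/3 + 1) / 4 = (4/3) / 4 = 33.3%.
- Cross-check by sequence: 2 of the 6 orders have two certain positions and 4 have one, so (2×2 + 4×1)/6 = 4/3 per block.
- Best guess: (1/2 + 2/3 + 2/3 + 1) / 4 = 70.8%, against 50% with no information.

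**Applied to 86 participants.** 86 is not a multiple of 4, so the result depends on how participants divide between the strata. The documents do not give that split, so all splits were covered.

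- If the strata leave remainders of 0 and 2, or 1 and 1, there are 21 complete blocks. The remaining two participants add nothing: 21 × 4/3 = 28.0, and 28.0/86 = 32.6%.
- If both strata leave a remainder of 3 (as 43 and 43 would), there are 20 complete blocks plus two third positions: 20 × 4/3 + 2 × 1/3 = 27.3, and 27.3/86 = 31.8%.

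The expected number of deducible allocations is therefore 27.3 to 28.0. With 43 per stratum, the best-guess rate is (10 × 17/6 + 1/2 + 2/3 + 2/3)/43 = 30.17/43 = 70.2%.

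**Alternatives.** These were simulated with an observer who knows the set of sizes but not their order, and who updates by Bayes' rule after each assignment. The assumption of 43 per stratum is for illustration; the plan's 43 is a per-arm figure.

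| Block sizes | Certain allocations | Best guess right |
|---|---|---|
| Fixed 4 | about 32% | about 70% |
| 4 and 6, random order | about 5.5% | about 69% |
| 4, 6 and 8, random order | about 2% | about 67% |

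**The case against.** The plan's concealment is real: a biostatistician generates the sequence, and the envelopes are numbered, sealed and opaque. Section N.2.1.1 places randomization after eligibility, and much of eligibility rests on scores, structured interviews or tests (ISI, CIWA, SCID, BOMC, sleep-apnea index, urine screen). That limits steering by judgement. It does not prevent timing of entry.

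Several stronger readings are tempting, and the documents do not support them.

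- **That the treating therapists are shown to be the recruiters.** The recruitment, consent and eligibility lists give a title in the plural, while the treating provider is a separate, singular entry. The identity is a strong inference, not a statement. Only the principal investigator's combination of roles is explicit.
- **That the principal investigator knows every past assignment.** The principal investigator is a backup therapist, and the names of the unblinded staff are removed from the text. Knowledge of all earlier assignments is not shown. The documents also do not say who opens the envelopes.
- **That the analysis can do nothing about it.** V.4.2 treats baseline variables found to be imbalanced as confounders, and the model contrasts changes from baseline. That addresses measured differences. Steering on unmeasured factors, such as motivation or expected adherence, would remain.
- **That varying the sizes nearly abolishes predictability.** It removes most of the certainty, but informed guessing falls only from about 70% to 69% or 67%.

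**Conclusion.** The point stands as an opportunity for selection bias; nothing in the documents shows that bias has occurred or that anyone would act on a prediction. About one third of allocations are deducible: 33.3% in complete blocks, and an expected 27 to 28 of 86 (about 32%) once incomplete last blocks are counted. Best guesses are right about 70% of the time. These figures assume full knowledge of the order of earlier assignments within the stratum, so they are an upper limit for anyone who knows less. The practical risk depends on how far the people who know assignments are also those who control entry. Because the improvement is cheap, it is worth making without evidence of intent.

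**What to change.** Have the biostatistician generate permuted blocks of randomly varying size, for example 4, 6 and 8, within each family-history stratum for all envelopes not yet used. Remove the sizes from L.2.2 and V.4.2 and keep them with the biostatistician, away from site staff.

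The cost is modest but not nil. A protocol change needs IRB authorization (V.2.1.3), and the list must be regenerated. If randomization has begun, the unused envelopes in both boxes must be replaced. The worst-case imbalance rises from 2 (half a block of 4) to 4 (half a block of 8) per stratum.

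Requiring eligibility to be signed and dated before the envelope is opened is an optional audit step. It leaves a record, but it does not by itself stop anyone deducing the next arm from earlier assignments.

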2.1. Provide

- 2.1.1. **The mode of data collection, e.g. telephone, in-person, questionnaire, interviews.** The initial screening will occur over the phone or in person using the IRB-approved telephone screening questionnaire (see attached telephone screen) similar to the one used in our CBT-I pilot study. Veterans who have positive screen will undergo baseline evaluations to further determine study eligibility. Once eligible they will be randomized into one of the study arms and treated for 8-weeks followed by a post-study follow up visits at 3 months and 6 months. All the assessments (in-person, questionnaires, and interviews) will occur during the baseline phase, treatment phase and post-study follow up phase, and will target evaluation of symptoms pertaining to sleep and insomnia, alcohol consumption (and other drugs if applicable), and psychiatric symptoms; see Table 1 for list of assessments and the time frame for their use, as well as Figure 1 for the study design. If the subject is unable to make it to the CMCVAMC during the week 8 time point or for the 3-month or 6-month follow-up, then the research team will complete the questionnaires with the subject over the phone or have the subject complete them at home via mailed questionnaire packet with telephone follow-up when necessary.
- 2.1.2. **The precise plan for how data is to be collected or acquired.** Most of the assessment measures will involve interviews (e.g. for the SCID form, or for the initial CBT-I session). During the treatment or follow-up phase, if the subject is unable to meet the research team at the CMCVAMC to complete the study questionnaires and interviews in-person, then the research team will complete the interviews and questionnaires by phone with the subject or have the subject complete the questionnaires via mailed packet and follow-up by telephone if any interviews are needed. The only exceptions to this rule are for the actigraphs and the portable sleep monitors. Actigraphs will be worn on the wrist for a few days at a stretch and the Veteran will be maintaining a sleep diary for the sleep-wake schedule. The monitor has sensors attached to the body recording oxygen saturation, airflow (nasal pressure), thoracic movements, snoring, body position and the heart rate. The apparatus measures nasal pressure, which is an accepted surrogate marker of air flow (instead of using oro-nasal thermistors, used in the earlier portable monitors); see Table 1 for details on the assessment measures and the time frames of assessments. All the staff conducting assessments will be blinded to the allocation of treatment arm with the exception of [name], the BSM treatment provider, [name] the person overseeing treatment allocation, and [name], the monitor for BSM treatment for the study. Overnight polysomnography data, will be obtained by the sleep technologist

at the CMCVAMC sleep center. The data will be captured electronically and will be analyzed by the physicians at the CMCVAMC VISN 4 Sleep Center sleep center as well as the research team.

Exact location where data will be collected. The initial screening will be conducted over the telephone or in person, either within the MIRECC office space of Room # 228 or in any available locked office space in the ARU/MHC on the 7th floor or 2nd floor of the main building. If the subject is unable to travel to the CMCVAMC for the week 8 or follow-up assessments, then the research team will complete them with the subject by phone or have the subject complete them via mailed packet with telephone follow-up if necessary. The source documents will be stored in the locked desk drawer of the study coordinator (in room # 228). All the rest of the source documents will be stored in the above-mentioned locked desk drawers of the study coordinator (in room # 228). Data from REDCap will be stored on VA servers located within a VA data center inside the VA firewall which afforded the same network protections as all VA sensitive clinical data. The electronic data, including any data pulled from REDCap see below for details Data from the actigraph will be stored locally on the desktop and backed up on compact disks and stored in the locked office drawer of the research assistant in the MIRECC office space with restricted access. Data from the polysomnographic sleep studies will be captured at the CMCVAMC Sleep Center. The data from the scored polysomnographic studies will be transferred via compact discs to the MIRECC VISN-4 secure databases.

- 2.1.3. Data management will occur through the VA REDCap (Research Electronic Data Capture), a secure web application and back-end database model, developed at Vanderbilt University with collaboration from a consortium of institutional partners. Approved study staff will enter data directly into REDCap, which obviates the need for transferring written data into electronic form; this significantly improves the quality of data. The VA has licensed its own version of REDCap housed on VA servers located within a VA data center inside the VA firewall and therefore afforded the same network protections as all VA sensitive clinical data. REDCap was developed specifically around HIPAA Security guidelines and is recommended to Penn Medicine researchers by our Office of Human Research. Relevant HIPAA-compliant features include password-protected access to the system, restriction of access to specific clinical trial data to designated users, audit trails of access and data updates, and built-in de-identification functions that can be used when exporting data for analysis. REDCap has been disseminated for use locally at other institutions and currently supports 170 academic/non-profit consortium partners on six continents and 13,000 research end-users (www.project-redcap.org). Approved study staff can access REDCap through a web-based interface and securely input data from any location at the time of data collection minimizing the need for travelling with either electronic or paper versions of sensitive information.

VA REDCap database administrators will have control over electronic access rights to REDCap databases. Only VA IRB approved individuals will be granted access to this database. This database keeps time-stamped information on people accessing, inputting, and altering data in the database.

- 2.1.4. **Exact location where data entry will take place.** Data entry will primarily take place in the locked office space of the MIRECC (room # 228B) which

has a restricted access to authorized staff only. Data entry may occur secondarily in the [name] locked office space (Room # 218, Bldg. 3), and in the available locked private office space of the ARU or the MHC on the seventh floor of the CMCVAMC main building. The PSG data will be acquired and evaluated at the CMCVAMC similar to other studies done in the past.

- 2.1.5. **The "title" of individual(s) collecting the data and analyzing the data, e.g. principal investigator, research coordinator.** Principal investigator ([name]), study coordinator, the behavioral sleep medicine provider, phlebotomy staff at the CMCVAMC laboratory services, and any other staff designated by [name] after approval of the CMCVAMC -IRB.

- 2.2. **Provide a time line for each aspect of the study.** See Table 2 for details related to the proposed activities associated with the study.

	Year 1				Year 2	Year 3	Year 4	Year 5			
	Q1	Q2	Q3	Q4				Q1	Q2	Q3	Q4
Set-up											
Enrollment											
Closeout of Study											
Education											
Data Analysis											
Dissemination											
Merit Review Application											

Q1 = 1st Quarter, Q2 = 2nd Quarter, Q3 = 3rd Quarter, Q4 = 4th Quarter

- 2.3. **Chart/Records/Data Review (retrospective and/or prospective)**
 - 2.3.1. Provide the planned or approximate number of charts/records/data to be accessed
 - 2.3.1.1. **CMCVAMC All subjects**
 - 2.3.1.2. Other site. N/A.
 - 2.3.2. **Does this protocol employ an Honest Broker?** YES NO
 - 2.3.2.1. If yes, provide name of individual. N/A
 - 2.3.2.2. **If no, explain who will access the charts/records.** Study-related staff; they will currently include [name], the study coordinator, and the behavioral sleep medicine specialist.
 - 2.3.2.3. **Describe from what database charts/records/data will be accessed.** Initial prescreening may be conducted by evaluating the CPRS (the electronic clinical charts of the patients) in order to alert their providers about the Veteran's option of participating in this study. After obtaining informed consent for the Veteran after he has signed the HIPAA form, we will access his clinical chart to evaluate for past and current clinical assessments and treatments as part of his/her baseline assessments.

- 3. **Future Use of Data and Re-Contact, if applicable.**
 - 3.1. **If any of the participant's data are going to be retained after the study for future research, the following information must be provided to the participant:** The blood sample for the genetic analyses. This explained in the informed consent form and the HIPAA form.

3.2. **Where will the data be stored?** The blood samples for the genetic analyses will be stored at a freezer space within the CMCVAMC (Research Building, 4th floor, freezer room), as designated by the CMCVAMC R & D staff. When all the samples have been collected and samples are ready for analyses we will transfer the samples with the coded identifier (and without any of the 17 HIPAA identifiers) from the CMCVAMC to the designated laboratory at the University of Pennsylvania after obtaining the required CMCVAMC -IRB authorization. The samples will be destroyed at the University of Pennsylvania after the genetic tests have been conducted.

3.2.1. **Who will have access to the data?** The Principal Investigator and the study coordinator and the regulatory agencies (CMCVAMC -IRB, and designated VA CS R & D staff). The staff associated with the genetic analyses laboratory and the statistician, both within the University of Pennsylvania will have access to the coded data (without the 17 HIPAA identifiers).

3.3. **If the subject is going to be re-contacted in the future about participating in future research, this must be specified. Describe the circumstances under which the participant would be re-contacted whether within the VA or outside the VA.** N/A

3.3.1. **If subjects will receive aggregate study results at the end of the study, the informed consent document must contain this information.** N/A

4. **Specimen Collection**

4.1. **Give the source of all specimens and whether they were collected for research, treatment or diagnosis.** Blood samples will be collected for genetic analyses related to research.

4.2. **State where specimens will be stored, secured and when discarded.** The blood samples for the genetic analyses will be stored at a freezer space within the CMCVAMC (Research Building, 4th floor, freezer room), as designated by the CMCVAMC R & D staff. When all the samples have been collected and samples are ready for analyses we will transfer the samples with the coded identifier (and without any of the 17 HIPAA identifiers) from the CMCVAMC to the designated laboratory at the University of Pennsylvania after obtaining the required CMCVAMC -IRB authorization. The samples will be destroyed at the University of Pennsylvania after the genetic tests have been conducted.

4.3. **Explain how destruction of samples will be substantiated.** The samples will be destroyed at the laboratory within the University of Pennsylvania using their standard protocols for destruction. A form certifying the destruction of the samples will be issued by the staff from the laboratory at the University of Pennsylvania.

O. **Genetic Testing, if applicable**

1. **Explain if the study is looking for an association between a genetic marker and a specific disease or condition, but at this point it is not clear if the genetic marker has predictive value.** The future study will explore for an association between single nucleotide polymorphisms (SNPs) of candidate genes and their relation with subjective and objective insomnia variables in the recovering alcoholic subjects. At this point it is not clear if the genetic marker has a predictive value.

1.1. The uncertainty regarding the predictive value of the genetic marker is such that studies in this category will not involve participant counseling.

1.2. Describe if the study is based on the premise that a link between a genetic marker and a specific disease or condition is such that the marker is clinically useful in predicting the development of that specific disease or condition. **N/A.**

1.3. Will the subject be notified of the results and the provision for genetic counseling?

Yes No N/A

1.3.1. If yes, explain further.

1.4. If biological specimens are used in this protocol, please respond to the following questions by checking the appropriate box:

	YES	NO	N/A
a. Does the project involve genetic testing?			
b. Will specimens be kept for future, unspecified use?			
c. Will samples be made anonymous to maintain confidentiality?			
d. Will specimens be destroyed after the project-specific use is completed?			
e. Will specimens be sold in the future?			
f. Will subjects be paid for their specimens now or in the future?			
g. Will subjects be informed of the results of the specimen testing?			
h. Are there any implications for family members based on specimen testing results? (If yes, they may be participants.)			
i. Will subjects be informed of results obtained from their DNA?			

